8.1.2 Secondary Efficacy Variables

Secondary endpoints for each cohort and for patients with solid tumours and MM will include:

- duration of response (DOR),
- time to response,
- time to progression,
- clinical benefit rate (CR [or sCR], PR [or VGPR] and stable disease [SD]),
- best overall response (BOR),
- PFS,
- overall survival (OS),
- IRC assessment of response rates focussing on Week 8, Week 16 and BOR for Cohort 1 (NSCLC) and other cohorts that demonstrate clinically meaningful efficacy per investigator assessment.

PFS is defined as the time from the first day of study treatment, until the first documented progression of disease or death from any cause, whichever occurs first. Patients with no PFS events will be censored at the time of the last evaluable tumour assessment. Patients with no tumour assessment after the baseline visit will be censored at the time of the first day of study treatment plus 1 day.

Overall survival (time to death) is defined as time between the first day of study treatment and date of death of any cause. Patients for whom no death is captured on the clinical database are censored at the most recent date they were known to be alive.

Time to progression is defined as time from the first day of study treatment to the first occurrence of progressive disease. Patients who have not progressed at the time of study completion (including patients who have died before progressive disease) or who are lost to follow-up are censored at the date of the last tumour assessment.

Clinical benefit response includes patients whose best response was:

- PR (or VGPR) or
- CR (or sCR) or
- Stable disease (SD) that have lasted at least 6 weeks.

For patients with response at Week 8, duration of response (unconfirmed) is defined as the period from the date of initial PR or CR until the date of progressive disease or death from any cause. Patients with no documented progression after CR or PR will be censored at the last date at which they are known to have had the CR or PR, respectively. The method for handling censoring is the same as described for the PFS.

For patients with a response at Week 8 of CR or PR, time to response is defined as the time from the first day of study treatment to the date of first CR or PR. The censoring rules will be similar to those of the PFS.

For patients with MM, responders will be defined as patients with CR, sCR, PR and VGPR status. All other definitions for secondary endpoints for these patients will be similar to definitions above.

The best (confirmed) overall response (BOR) will be also assessed at the end of Stage II for each cohort. BOR is defined as the best response recorded from the first day of study treatment until disease progression/recurrence or death. To be assigned a status of PR or CR (i.e., a responder), changes in tumour measurements must be confirmed by repeat assessments that should be performed no less than 4 weeks after the criteria for response are first met, i.e., patients need to have two consecutive assessments of PR or CR to be a responder. Only patients with measurable disease at baseline will be included in the analysis of the BOR. Patients without a post-baseline tumour assessment will be considered to be non-responders. Duration of confirmed response is defined as the period from the date of initial PR or CR that contributed for the BOR status until the date of progressive disease or death from any cause. Patients with no documented progression after CR or PR will be censored at the last date at which they are known to have had the CR or PR, respectively. The method for handling censoring is the same as described for the PFS.

For responders in BOR, time to response is defined as the time from the first day of study treatment to the date of first CR or PR. The censoring rules will be similar to those of the PFS.

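### Both duration-of-response definitions count death as an event, but the next sentence literally censors responders who die without documented progression

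*Protocol*

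**What the plan says.** All the relevant text is in Protocol Section 8.1.2.

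- **DOR event.** For patients with a response at Week 8, DOR is "the period from the date of initial PR or CR until the date of progressive disease or death from any cause". Confirmed DOR, defined later in the section with best overall response, has the same end point.
- **DOR censoring, first sentence.** "Patients with no documented progression after CR or PR will be censored at the last date at which they are known to have had" their response. It follows both definitions.
- **DOR censoring, second sentence.** "The method for handling censoring is the same as described for the PFS". It also follows both definitions.
- **PFS event.** PFS runs "until the first documented progression of disease or death from any cause, whichever occurs first".
- **PFS censoring.** "Patients with no PFS events will be censored at the time of the last evaluable tumour assessment". Then: "Patients with no tumour assessment after the baseline visit will be censored at the time of the first day of study treatment plus 1 day".
- **TTP, for contrast.** Patients who die before progressive disease are expressly listed among those censored.

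The definitions for multiple myeloma are said to be similar. Section 8.3.2 has these endpoints estimated by Kaplan-Meier with 95% confidence intervals.

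**The concern.** The first DOR censoring sentence selects patients by the absence of documented progression, not by the absence of an event. A responder who dies without a progression assessment has had an event by definition, yet falls in the group to be censored. The cross-reference to PFS then points to a rule that treats the same patient as an event. Two analysts following the section could report different DOR curves from the same data.

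Death without documented progression is foreseeable here. Section 7.2.1.4 allows that, when progression is clinically evident, the investigator may do no further disease assessments. Cohorts are also small. The Stage II success thresholds in Table 16 are 5 responders of 19 or 6 of 13, so a single such death can be a sizeable share of all DOR events. With no control arm, an upward bias in DOR has no comparator to set it against.

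**Working it through.** **Step 1: apply the three DOR sentences to four kinds of responder.**

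| Responder | Event definition | Sentence on no documented progression | PFS rule by cross-reference |
|---|---|---|---|
| Documented progression | event | not censored | event |
| Dies, no documented progression | event at death | censored at last CR/PR | event at death |
| Alive, last evaluable scan CR/PR | no event | censored at that scan | censored at that scan |
| Alive, last evaluable scan neither CR/PR nor PD | no event | censored at the earlier CR/PR scan | censored at the later scan |

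The second row is a conflict of event status and the fourth a conflict of date. The fourth row can occur under Appendix 4: a later scan may no longer be 30% below baseline without being 20% above the nadir.

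**Step 2: direction of each conflict.**

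- *Status.* Turning an event into a censored time removes a downward step from the Kaplan-Meier curve, so the curve rises.
- *Date.* The last CR/PR date is never later than the last evaluable assessment. Earlier censoring leaves fewer patients at risk when later events occur, so it can only leave the curve unchanged or lower it.

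**Step 3: size of the status conflict.** The protocol gives no figure to reproduce, so this is an illustration. Assume constant hazards, a true median m, and a share f of events that are deaths without documented progression.

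- Total hazard: λ = ln 2 / m
- Progression hazard, which is all that remains when those deaths are censored: (1−f)λ
- Apparent median: ln 2 / [(1−f)λ] = m / (1−f)

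Take m = 6.7 months, the median DOR reported for the phase II melanoma study in Section 1.3.4.2 (an assumption for this trial). The six-month Kaplan-Meier values come from a simulation of 400,000 responders. It used exponential times, scans every 8 weeks, progression dated at the next scan, and deaths either counted or censored at the last scan.

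| f (assumed) | Factor 1/(1−f) | Median, months | Six-month DOR, deaths as events | Six-month DOR, deaths censored |
|---|---|---|---|---|
| 5% | 1.05 | 6.7 → 7.1 | 0.56 | 0.58 |
| 10% | 1.11 | 6.7 → 7.4 | 0.56 | 0.60 |
| 20% | 1.25 | 6.7 → 8.4 | 0.56 | 0.63 |
| 30% | 1.43 | 6.7 → 9.6 | 0.56 | 0.66 |

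The medians are from the formula. Simulated medians move in 8-week steps and are less informative.

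**Step 4: what f could mean here.** If all 5 responders in a cohort of 19 have an event, one such death gives f = 1/5 = 20%. In a cohort expanded to 70 with 28 responders (the 40% case in Table 17), and again all with an event, it gives f = 1/28 = 3.6% and a factor of 28/27 = 1.04. The factor is a large-sample quantity. In a handful of responders the observed median could move by more, by less or not at all.

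**The case against.** The strongest reply is that the intent is clear. The event definition comes first and includes death. The cross-reference leads to a rule that censors only patients without an event. For TTP, where deaths are meant to be censored, the protocol says so. Detailed censoring rules also commonly sit in an SAP, which is not shown here.

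Most of this stands as evidence that the authors probably meant death to count. It does not remove the conflict. The first censoring sentence, read as written, still covers deaths, it appears twice, and it gives a date that the cross-reference contradicts. This is a statement at odds with its neighbours, not detail left for later.

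A reader might go further and infer two things that the text does not support.

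- *That PFS is contradictory in the same way, so that deaths before the first 8-week scan are censored at Day 1 plus 1.* On that reading, 3 such deaths among 19 patients would turn an 8-week PFS of 16/19 = 84% into 100%. But the Day 1 plus 1 sentence directly follows the one on patients with no PFS events. It reads naturally as the date for those among them who have no assessment to use. A patient who has died already has an event. The sentence merits a clarifying phrase, not a claim of bias.
- *That dating the censoring at the last CR/PR also inflates DOR.* Step 2 shows that it does not.

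**Conclusion.** The point holds for both DOR definitions. As written, Section 8.1.2 makes death without documented progression both an event and a reason for censoring, and gives two censoring dates. Following the censoring sentence literally biases DOR upward. The median rises by about 11% if one event in ten is such a death and by 25% if one in five is. This rests on constant hazards and on assumed values of f, because the protocol gives nothing from which to estimate f. The conflict of dates affects reproducibility only.

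The reach is limited. DOR is a secondary endpoint, summarised without a hypothesis test. The Week 8 response rate, the Stage I and II rules and OS do not depend on it. The correction is worth making but does not touch the trial's main conclusions.

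**What to change.** For both DOR definitions, state that progression or death from any cause is an event, and that responders with neither are censored at the last evaluable tumour assessment, as for PFS. Delete the sentence that censors at the last date of known CR or PR. As a minor clarification, limit the PFS Day 1 plus 1 rule to patients with no PFS event, that is, not known to have died.

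The cost is wording only, with no new data or visits. The one downside is that DOR may look slightly shorter than under the literal censoring sentence.

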Rules for Stage II:

A study treatment will be considered to be efficacious in a cohort in Stage II if

- there is no unacceptable toxicity and
- the number of responders is equal or above the specified number in the sample size calculations, as presented in [Table 2](#) or
- best overall response, BOR (confirmed) is higher than 15%.

Cohort Expansion

There will be no formal statistical hypothesis tested as part of the expansion cohort analysis. The analysis of the expanded cohort will allow estimation of RR and other efficacy parameters and other efficacy parameters (please refer to secondary efficacy parameters in [Section 8.1.2](#)) with increased precision and more insight concerning the safety profile.

Efficacy Data Analyses

The primary efficacy endpoint is RR at Week 8 in each cohort, as assessed by the Investigator using RECIST, v1.1 or IMWG response criteria. This is an early phase II study and cohorts are independent, hence there will be no adjustment for multiplicity. Number and percentage of responders with corresponding Clopper-Pearson 95% confidence intervals will be provided for each cohort. The overall response rate will be assessed via BOR. The clinical benefit rate and BOR will be analysed in a similar way to RR.

Duration and time of response in each indication will be summarized only for responders, i.e., for the patients whose confirmed response is CR or PR for patients with solid tumours and CR, sCR, VGPR or PR for patients with MM.

Estimates for the survivor function for the time-to-event variables, such as time to progression (TTP), PFS,

OS, duration of response, and time to response, will be obtained by using the Kaplan-Meier (KM) approach together with associated 95% CI.

Due to the small sample size in Cohort 7 (patients with other solid tumours), only descriptive statistics will be applied. If there are at least 5 patients with the same tumour type, number (percentage) of patients will be summarized in the frequency table and listed for RR at Week 8, clinical benefit rate and BOR. If there are fewer patients, only listings will be provided. For response criteria for patients with prostate cancer, ECD and/or LCH enrolled in this cohort, see [Appendix 9](#) and [Appendix 10](#), respectively.

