5.3.6 Response Criteria

5.3.6.1 Solid tumours

Response of measurable solid tumours to study treatment will be evaluated by the Investigator according to RECIST, v1.1 criteria ([Appendix 4](#)) (67). See [Appendix 9](#) for prostate, [Appendix 10](#) for ECD and/or LCH specific response criteria.

Tumour evaluations will occur once during the Screening Period (Days –28 and –1), every 8 weeks after starting vemurafenib during the Treatment Period, and at the End of Treatment Visit. A window of \pm 5 days of scheduled visit is allowed to complete the tumour assessments at the required intervals.

Radiological tumour assessments to measure extent of disease will be carried out by CT/MRI of the chest/abdomen/pelvis (C/A/P) for all patients. In addition, CT/MRI of the brain can be performed if clinically indicated and as per standard care.

Patients should be assessed at the designated time points using a consistent imaging modality. The same imaging technique must be used for a patient throughout the study. The same method of assessment and the same technique should be used to characterize each identified and reported lesion at baseline and during follow-up. If more than one method of assessment is used at baseline, the most accurate method according to RECIST should be selected when recording data; in addition, this method should be performed in all subsequent evaluations. Tumour measurements should be made by the same Investigator/radiologist for each patient during the study to the extent that this is feasible.

For solid tumours to be assigned a status of partial response (PR) or complete response (CR) (i.e., a responder), changes in tumour measurements must be confirmed by repeat assessments performed no less than 4 weeks after the criteria for response are first met, i.e., patients need to have two consecutive assessments of PR or CR to be a responder.

Symptomatic deterioration may indicate progressive disease (PD). However, radiological confirmation of PD is strongly recommended.

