5.3.6.2 Multiple myeloma

Response of MM to study treatment will be evaluated according to IMWG uniform response criteria ([Appendix 5](#)) ([68, 69](#)).

Evaluations will occur once during the Screening Period (Days -28 and -1), 8 weeks after starting vemurafenib, every 28 days thereafter during the Treatment Period, and at the End of Treatment Visit.

Serum M-protein level will be quantitated using densitometry on serum protein electrophoresis (SPEP) by immunofixation.

Urine M-protein measurement will be estimated using 24-hour urine protein electrophoresis (UPEP) only. Random or 24-hour urine tests measuring kappa and lambda light chain levels are not reliable and are not recommended. For oligosecretory and light chain myeloma patients, serum free light chains will be measured.

Patients will need to have two consecutive assessments of CR, sCR, VGPR or PR to be considered a responder.

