8.3.2 Efficacy Data Analysis

The primary efficacy endpoint is RR at Week 8 in each cohort, as assessed by the Investigator using RECIST, v1.1 or IMWG response criteria.

This is an early phase II study and cohorts are independent, hence there will be no adjustment for multiplicity.

Number and percentage of responders with corresponding Clopper-Pearson 95% confidence intervals will be provided for each cohort. The clinical benefit rate, BOR and RR at the end of Stage II will be analysed in a similar way to RR at Week 8. Estimates for the survivor function for the time-to-event variables, such as time to progression (TTP), PFS, OS, duration of response, and time to response, will be obtained by using the Kaplan-Meier (KM) approach together with associated 95% CI.

Due to the small sample size in Cohort 7 (patients with other solid tumours), only descriptive statistics will be applied. If there are at least 5 patients with the same tumour type, number (percentage) of patients will be summarized in the frequency table and listed for RR at Week 8, clinical benefit rate and BOR. If there are fewer patients, only listings will be provided. For response criteria for patients with prostate cancer, ECD and/or LCH enrolled in this cohort, see [Appendix 9](#) and [Appendix 10](#), respectively.

In case a cohort/indication is expanded up to 70 patients, the primary analysis for efficacy will occur once all patients have been followed up for 9 months after last patient had been enrolled in that cohort, or the patient develops progressive disease, withdraws consent, or is lost to follow-up, whichever occurs first.

For all patients in Cohort 1, the CT scans during the patient's last therapy prior to this study, as well as CT scans made during this study, will be collected and reviewed retrospectively by an IRC. Scans from the prior therapy will be used to establish pITT, and this may be examined in relation to the TTP achieved from study treatment. During the study, the investigator-assessed response rate will remain as the primary efficacy endpoint and the IRC assessment will be a supportive secondary endpoint. The concordance tables between Investigator and IRC assessment will be produced. The IRC assessment of response rates will focus on Week 8, Week 16 and BOR. For other cohorts, collection of scans are described in the study assessment sections. Analyses will be performed as described above for Cohort 1.

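### Time to response for Week 8 responders (Section 8.1.2) can only return the date of the Week 8 assessment, and it conflicts with the synopsis restriction to confirmed responders

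*Protocol*

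**What the plan says.** Time to response is a secondary objective (Section 2.2) and a secondary endpoint for every cohort (Section 8.1.2). The protocol fixes the following.

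- **Week 8 version (8.1.2).** "For patients with a response at Week 8 of CR or PR, time to response is defined as the time from the first day"; the end point is the first recorded CR or PR. The accompanying duration of response for the same patients is labelled unconfirmed.
- **BOR version (8.1.2).** "For responders in BOR, time to response is defined as the time from the first day of study treatment", with the same end point. BOR responders need confirmation at least 4 weeks later.
- **Censoring (8.1.2).** Both versions carry the sentence "The censoring rules will be similar to those of the PFS".
- **Estimator (8.3.2).** Survivor functions for several variables, including "duration of response, and time to response, will be obtained by using the Kaplan-Meier (KM) approach together with associated 95% CI".
- **Synopsis, Efficacy Data Analyses.** "Duration and time of response in each indication will be summarized only for responders", and the sentence goes on to specify confirmed response.
- **Schedule.** Solid tumours are assessed at screening and then "every 8 weeks after starting vemurafenib during the Treatment Period" (5.3.6.1, with a 5-day window either side). Myeloma is assessed at screening and then "8 weeks after starting vemurafenib, every 28 days thereafter during the Treatment Period" (5.3.6.2). The bone-scan guidance for prostate cancer and ECD/LCH (Appendices 9 and 10) also treats Cycle 3 Day 1 as the first scan.

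**The concern.** The Week 8 version selects patients by their status at the first scheduled assessment and then asks when they first responded. The selection already contains the answer. A median and 95% CI would be printed for each cohort and could be read as information about how quickly the drug works, when they describe only when the scan was booked.

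A comparison invited by the protocol shows the risk. Section 1.3.4.3 reports a median time to response of 1.45 months for vemurafenib in the phase III melanoma trial, and Section 1.3.4 makes reproducibility of the melanoma data in other indications a primary goal. A reader who set the two side by side could take a difference in scan timing for a difference in drug effect.

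The synopsis and Section 8.1.2 also disagree on whose time to response is to be summarised.

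**Working it through.** The protocol states no expected value for time to response, so there is no figure to reproduce.

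**1. Date of the first assessment.** A cycle is 28 days (Section 3.1), so Week 8 is Cycle 3 Day 1: 1 + 2 × 28 = Day 57. With the 5-day window, 57 − 5 = 52 and 57 + 5 = 62. If the 1-day visit window for Cohort 3b (Section 5.3.2) governs, the range is Days 56 to 58. In Part 1 of that cohort vemurafenib starts on Day 2, which may move the target by a day.

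**2. Who is in the set, and when is their event?** Section 8.1.1 defines Week 8 responders by their status at Week 8. No earlier assessment is scheduled, so the first CR or PR is that assessment. Requiring later confirmation would not change its date.

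**3. Who can be censored?** Membership requires the event, so the number censored is 0 in both versions. The PFS-like rule applies to nobody, and Kaplan-Meier reduces to the empirical distribution of event dates.

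**4. Does the result react to the drug?** A simulation with assumed inputs (not protocol figures) used 200,000 patients per scenario. Scans fell every 56 days from Day 57 with a uniform jitter of up to 5 days. True onset was exponential with a median of 7 to 84 days, and 20% or 45% of patients ever responded. Confirmation, progression and death were not modelled, so the third column only approximates the BOR version. The results for 45% ever responding were:

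| True median onset (days) | Week 8 version: median (range) | All responders: median | All patients: responded by Day 62 | By Day 118 |
|---|---|---|---|---|
| 7 | 57 (52–62) | 57 | 44.7% | 44.9% |
| 28 | 57 (52–62) | 59 | 33.7% | 42.1% |
| 56 | 57 (52–62) | 62 | 22.5% | 33.8% |
| 84 | 57 (52–62) | 112 | 16.7% | 27.3% |

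With 20% ever responding, the Week 8 version again gave Day 57 (52–62). Across all scenarios the Week 8 response rate ran from 7.3% to 44.7% while that median did not move.

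**5. What the BOR version does and does not show.** It can take later scan dates, and in the table its approximation moves from Day 57 to Day 112. It does not show how many respond. Suppose first responses occur in 30%, 10% and 5% of patients at Weeks 8, 16 and 24 (45% in all). Among responders this gives 30/45 = 67%, 10/45 = 22% and 5/45 = 11%. A cohort with one third of each (15% in all) gives the same three figures.

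**6. The melanoma comparison.** The shortest on-schedule value is 52 − 1 = 51 elapsed days, or 51/30.44 = 1.7 months. The melanoma median of 1.45 months is 1.45 × 30.44 = 44 days. An on-schedule median in this study cannot be that short, however fast the drug acts. The protocol does not give the melanoma trial's scan schedule.

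**The case against.** The strongest reply is that the synopsis already governs. It restricts the summary to confirmed responders, so the degenerate version might never be reported. That does not remove the problem: Section 8.1.2 still defines the Week 8 version, Section 8.3.2 assigns Kaplan-Meier to time to response without separating the two, and the synopsis therefore contradicts Section 8.1.2. It does support making confirmed responders the single definition.

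A reader might go further and infer that time to response as a whole cannot tell an active cohort from an inactive one, or that any responders-only summary is an error calling for competing-risk methods. The documents do not support that. The BOR version can take later dates and describes speed given response, which is customary. Section 1.3.4.3 quotes medians of 1.45 and 2.7 months with confirmed response in 48% and 5% of patients. With fewer than half responding, these medians can only be among responders, yet they differ. How many respond is covered separately by Week 8 response rate and BOR with exact intervals. The identical curves in step 5 of the working arise because one cohort was made exactly proportional to the other.

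It is also fair to say that an unused censoring sentence changes no estimate, that Kaplan-Meier without censoring is harmless in itself, and that time to response enters no stage, efficacy or expansion rule. These points limit the weight of the finding. The analysis plan could settle the choice of estimator, but the protocol itself fixes the patient set, origin, event and censoring rule that produce the degeneracy.

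**Conclusion.** The point holds for the Week 8 version only. On schedule, its values are the Week 8 assessment dates, about Days 52 to 62, with no censoring and no information on speed of response. It cannot serve the secondary objective it is listed under. The conflict with the synopsis over confirmed response also stands.

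The range assumes a Week 8 assessment within its window and no earlier one, whether unscheduled or at an early End of Treatment Visit. It may be narrower in Cohort 3b. Departures from schedule would add scatter but would still reflect when patients were scanned.

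The BOR version remains usable: it is limited by the 8-week scan interval in solid tumours (28 days after Week 8 in myeloma) and conditional on response, but not fixed by the schedule. The primary endpoint, the two-stage rules and the sample size are untouched. The change is worth making because it is nearly free, but no decision in the trial depends on it.

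**What to change.** - **Section 8.1.2:** delete the Week 8-responder definition of time to response. Keep the definition for confirmed (BOR) responders, and remove the PFS-like censoring sentence attached to time to response.
- **Section 8.3.2 and the matching synopsis text:** take time to response out of the Kaplan-Meier list. Report first-response timing in BOR responders descriptively as counts by assessment: Weeks 8, 16, 24 and later for solid tumours, and the 28-day assessments after Week 8 for myeloma. State that the summary is conditional on response and limited by the assessment interval.
- **Synopsis:** retain the restriction to confirmed responders so that it agrees with Section 8.1.2.
- **Optional:** add the cumulative incidence of first confirmed response in all patients of the response analysis set, with progression or death before response as competing events. This adds a display that reflects both how many respond and how soon. It is an improvement rather than the correction of an error, and its plateau will largely repeat the BOR rate.

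The cost is a few sentences in two sections and the synopsis. It needs no new data, visits or patients.
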